12.8. Pharmacodynamic Endpoints (Cohort 1 only)

The following pharmacodynamics endpoints will be determined:

- Median time to onset of sensory block and motor block

- Median duration of sensory block and motor block

12.9. Appropriateness of Measures

Endpoints selected for this study were based on validated methodologies and other well-established clinical measurements used in the peer reviewed literature. Measurements were further refined in this study based on previous nerve block experience with EXPAREL and other Phase 3 or 4 studies.

13. STUDY PROCEDURES

A time and events schedule for all study procedures is provided in [Table 1](#) and [Table 2](#).

13.1. Instructions for Conducting Procedures and Measures

All PK, sensory/motor function assessments, and safety assessments conducted after baseline (predose) will be timed from the end of the block. End of block procedure is defined as the time of completion of study drug administration after combined sciatic (in popliteal fossa) and saphenous (in the adductor canal) nerve blocks.

At timepoints when multiple assessments coincide, assessments will be performed in the following sequence: pain intensity assessment, sensory assessments, motor assessment, blood draw for PK assessment as applicable.

The **start of surgery** is defined as the time of the first incision. The **end of surgery** is defined as the time recorded in the surgical record. **Postsurgical** is defined as after the end of surgery.

Postsurgical analgesia and collection of study data through the primary endpoint will take place under the supervision of study staff at the site.

Subjects will be provided an e-diary on the day of surgery and instructed on duties and responsibilities with the e-diary.

13.1.1. Pain Intensity Assessment

Pain intensity will be assessed using an 11-point NRS (0-10) as follows:

- Pain intensity scores (using the NRS) measured as “How much pain are you experiencing right now?” will be assessed:
 - Upon arrival in the PACU (± 5 min)
 - Every 15 mins in the PACU (± 5 min)
 - Prior to PACU discharge (± 5 min)
 - Every 6 hours from the end of surgery until 96 hours: 6 h (± 2 h), 12 h (± 2 h), 18 h (± 2 h), 24 h (± 2 h), 30 h (± 2 h), 36 h (± 2 h), 42 h (± 2 h), 48 h (± 2 h), 54 h (± 2 h), 60 h (± 2 h), 66 h (± 2 h), 72 h (± 2 h), 78 h (± 3 h), 84 h (± 3 h), 90 h (± 3 h), and 96 h (± 3 h)

- If a subject is asleep, the subject will not be awakened to assess pain. If the subject awakens within the assessment window, a pain score will be collected then
- Subjects will be instructed not to complete the NRS pain intensity score after any physical activity, including the motor block assessment. If that is not possible, to assess pain intensity at rest, the subject should rest quietly in a supine or seated position that does not exacerbate his or her postsurgical pain for 5-10 minutes before entering the pain score using the NRS. Subjects will also be required to provide unscheduled pain assessments prior to consumption of any breakthrough pain medication.
- An unscheduled NRS assessment will be obtained immediately prior to administration of any breakthrough pain medication until 96 hours post-surgery.
- Pain intensity scores (NRS) once daily at 21:00 (± 3 h) from POD 1 to POD 14 measured as “What was your **worst** pain in the last 24 hours?”
- Pain intensity scores (NRS) once daily at 21:00 (± 3 h) from POD 1 to POD 14 measured as “What was your **average** pain in the last 24 hours?”

Subjects will be instructed to focus all NRS pain intensity ratings on the operative ankle/foot, and not other locations where they may be experiencing pain.

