
have at least 90% power to detect a true difference of 150-units in the AUCs. Therefore, since Cohort 1 will have 60 subjects (20 EXAPREL, 20 EXPAREL admixed with bupivacaine HCl and 20 bupivacaine HCl), Cohort 2 will need to enroll 60 subjects (20 EXAPREL, 20 EXPAREL admixed with bupivacaine HCl and 20 bupivacaine HCl) to meet the total requirements.
 
An efficacy interim analysis will occur when approximately 60 subjects have enrolled and provided complete data for the primary efficacy outcome.
		

Table 1: Time and Events Schedule of Study Procedures (Screening through Day 14)

	Screening Visit ¹	Day of Surgery Prior to Nerve Block	O	P A C U	Time from End of Surgery (h)																Health Care Facility Discharge ²	PO D 14 Call ±3 days					
					6 ±2	12 ±2	18 ±2	24 ±2	30 ±2	36 ±2	42 ±2	48 ±2	54 ±2	60 ±2	66 ±2	72 ±2	78 ±3	84 ±3	90 ±3	96 ±3							
Obtain ICF*	X																										
Assess/confirm eligibility *	X	X																									
Record medical/surgical history*	X																										
Collect height/weight for BMI calculation*	X																										
Demographics and baseline characteristics*	X																										
Administer Pain Catastrophizing Scale	X																										
Record prior and concomitant medications	X	X	←																								→
Provide e-diary and explain expectations		X ³																									
Urine pregnancy test for WOCBP ⁴	X	X ³																									
Record worst and average pain (NRS) in the last 30 days		X ³																									
Randomize subject; prepare study drug.		X																									
Record block start/end times ⁵		X																									
Record surgery start and end times			X																								
Record intra-op medication administered			X																								
Record PACU time in and out				X																							
Record scheduled NRS scores ^{6,7}				X ⁷	X	X	X	X	X	X	X	X	X	X	X	X	X	X	X	X	X	X	X	X	X	X	X

7. Pain scores (24 h recall) once daily (i.e., worst/average pain) will be collected at 21:00 (± 3 hours) from POD 1 to POD 14. Pain scores (current pain) will be collected beginning at PACU admission (± 5 min); q15 min in PACU (± 5 min); at PACU discharge (± 5 min) ; then q6h (± 2 h) from end of surgery to 72 hours post-surgery and q6h (± 3 h) from 78-96 hours post-surgery.

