13.7. Postsurgical Assessments from End of Surgery through Discharge

-
- Record pain intensity scores (NRS) (see Appendix 1, [Section 18.1](#)) measured as “How much pain are you experiencing right now?” from the end of surgery to 96 hours post-surgery as follows:
 - Every 6 hours from the end of surgery to 96 hour post-surgery, i.e., 6 h (± 2 h), 12 h (± 2 h), 18 h (± 2 h), 24 h (± 2 h), 30 h (± 2 h), 36 h (± 2 h), 42 h (± 2 h), 48 h (± 2 h), 54 h (± 2 h), 60 h (± 2 h), 66 h (± 2 h), 72 h (± 2 h), 78 h (± 3 h), 84 h (± 3 h), 90 h (± 3 h), and 96 h (± 3 h).
 - If a subject is asleep, the subject will not be awakened to assess pain. If the subject awakens within the assessment window, a pain score will be collected then.
 - Subjects will be instructed not to complete the NRS pain intensity score after any physical activity, including the motor block assessment. If that is not possible, to assess pain intensity at rest, the subject should rest quietly in a supine or seated position that does not exacerbate his or her postsurgical pain for 5-10 minutes before entering the pain score using the NRS.
 - An unscheduled NRS assessment will be obtained immediately prior to administration of any breakthrough pain medication until 96 hours post-surgery.
- Record pain intensity scores (NRS) measured as “What was your worst pain in the last 24 hours?” and “What was your average pain in the last 24 hours?”
 - Once daily at 21:00 (± 3 h) starting on POD 1.
- Subject to record satisfaction with pain management using 1 question from the International Pain Outcome (IPO) questionnaire at 96 hours (± 3 h) post-surgery.
- For Cohort 1 only:
 - Collect scheduled PK blood sample(s).
 - Perform sensory and motor function assessments.
- Record AEs/ SAEs.
- Record concomitant medications for treatment of AEs/ SAEs.

To mitigate the risk from falls, subjects will be required to be non-weight bearing for at least 2 weeks post-surgery, unless the investigator determines a limited touch down or partial weight bearing for balance with a walker assist device is more appropriate to reduce the risk of fall.

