The beginning of surgery is defined as the time of the first incision.

End of Surgery

The end of surgery is defined as the time recorded in the surgical record.

Postsurgical

Postsurgical is defined as after the end of surgery.

Time Window for Numeric Rating Scale (NRS) for Scheduled Pain Score Collection

Table below provides the time window for the NRS pain score for analysis. If multiple scheduled or unscheduled assessments occur within the same window, the assessment closest to the scheduled time will be chosen. If the assessments are equidistance the later will be chosen.

Scheduled Time of Collection	Time Window for Acceptable Actual Time of Collection
6-hour	From PACU arrival to 9-hour
12-hour	From >9-hour to 15-hour
18-hour	From >15-hour to 21-hour
24-hour	From >21-hour to 27-hour
30-hour	From >27-hour to 33-hour
36-hour	From >33-hour to 39-hour
42-hour	From >39-hour to 45-hour
48-hour	From >45-hour to 51-hour
54-hour	From >51-hour to 57-hour
60-hour	From >57-hour to 63-hour
66-hour	From >63-hour to 69-hour
72-hour	From >69-hour to 75-hour
78-hour	From >75-hour to 81-hour
84-hour	From >81-hour to 87-hour
90-hour	From >87-hour to 93-hour
96-hour	From >93-hour to 99-hour

 Table 3. Time Window for the NRS Pain Score Collected at Scheduled Time Points Post-Surgery

Time Window for Sensory and Motor Block Tests

Table below provides the time window for the sensory block and motor block summaries by timepoint (Sections 9.7.1 and 9.7.1).

Scheduled Time of Collection	Time Window for Acceptable Actual Time of Collection
Predose	Predose
15-min	From end of study drug administration to 22.5-min
30-min	From >22.5-min to 37.5-min
45-min	From >37.5-min to 52.5-min
1-hour	From >52.5-min to 1.5-hour
2-hour	From >1.5-hour to 5-hour
8-hour	From >5-hour to 10-hour
12-hour	From >10-hour to 18-hour
24-hour	From >18-hour to 27-hour
30-hour	From >27-hour to 39-hour
48-hour	From >39-hour to 54-hour
60-hour	From >54-hour to 66-hour
72-hour	From >66-hour to 78-hour
84-hour	From >78-hour to 90-hour
96-hour	From >90-hour to 108-hour
120-hour	From >108-hour to 132-hour
144-hour	From >132-hour to 156-hour
168-hour	From 156-hour to 180-hour

Table 4. Time Window for the Sensory and Motor Block Tests at Scheduled Time Points Post-Study Drug Administration

Oral Morphine Equivalent Dose (OMED)

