6. STUDY ASSESSMENTS

6.1. Efficacy Assessment

6.1.1. Pain Intensity Assessment

- Pain intensity scores measured using NRS as "How much pain are you experiencing right now?" * will be assessed as follows:
 - Upon arrival in the Post-Anesthesia Care Unit (PACU)
 - At 15-minute intervals in the PACU
 - At to PACU discharge
 - Every 6 hours from the end of surgery to 96 hours postsurgery as follows: 6 h, 12 h, 18 h, 24 h, 30 h, 36 h, 42 h, 48 h, 54 h, 60 h, 66 h, 72 h, 78 h, 84 h, 90 h, and 96 h.
 - Prior to administration of any pain medication until 96 hours post-surgery
- Pain intensity using the NRS once daily at 21:00 (±3 h) from POD 1 to POD 14 measured as "What was your **worst** pain in the last 24 hours?"
- Pain intensity using the NRS once daily at 21:00 (±3 h) from POD 1 to POD 14 measured as "What was your **average** pain in the last 24 hours?"

* If subject is asleep, the subject will not be awakened to assess pain. If the subject awakens within the time window, a pain score will be collected then.

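### Up to 72 h a subject who sleeps through the ±2 h collection window is not asked for a pain score that the SAP's ±3 h window would accept; collecting on waking up to +3 h is a cheap, small improvement.

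*Protocol*

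**What the plan says.** **Sleep rule.** Protocol 13.7 states: "If a subject is asleep, the subject will not be awakened to assess pain". Protocol 13.1.1 adds: "If the subject awakens within the assessment window, a pain score will be collected then". Appendix 1 repeats both. SAP 6.1.1 carries its own version: "If the subject awakens within the time window, a pain score will be collected then". It does not say which window is meant.

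**Collection windows.** Protocol Table 1, footnote 7, sets current-pain scores after the PACU as: "then q6h (± 2 h) from end of surgery to 72 hours post-surgery and q6h (± 3 h) from 78-96 hours post-surgery". Sections 12.1, 13.1.1, 13.7 and Appendix 1 list the same limits slot by slot.

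**Analysis windows.** SAP Section 5, Table 3, uses adjoining windows. The 12 h slot is "From >9-hour to 15-hour" and the 72 h slot is "From >69-hour to 75-hour", so both are ±3 h, and this holds for every slot from 12 h to 96 h. The 6 h slot differs: "From PACU arrival to 9-hour". Unscheduled scores can also fill a slot.

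**Use of the scores.** Under SAP 9.5.1 the AUC takes all scores from PACU arrival to 96 h at their exact times. Under SAP 9.2.2 a slot still empty after windowing gets the worst value if it lies in an opioid window (wWOCF), and otherwise a multiply imputed value.

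**The concern.** The protocol asks for scores over a narrower span than the SAP is prepared to use, and the sleep rule makes that difference count. An awake subject can be scored on time. A sleeping subject can be scored only on waking, and if waking comes just after the window closes no scheduled score is requested. For daytime surgery the first three nights fall under the ±2 h window; the ±3 h window starts only at 78 h.

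What is at stake is avoidable missing data in the primary endpoint. Whether a subject sleeps through a window plausibly depends on pain, and the imputation model in SAP 9.2.2 contains only the 16 scheduled scores, run by treatment, with nothing about sleep. A score taken on waking is real data that the analysis already accepts.

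**Working it through.** **1. The windows side by side (hours after end of surgery).**

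| Slot | Protocol collection | SAP Table 3 | Late hour accepted but not asked for |
|---|---|---|---|
| 6 h | 4 to 8 | PACU arrival to 9 | 8 to 9 (PACU scores can fill this slot) |
| 12 h | 10 to 14 | >9 to 15 | 14 to 15 |
| 18 h | 16 to 20 | >15 to 21 | 20 to 21 |
| each slot t from 24 h to 72 h | t−2 to t+2 | >t−3 to t+3 | t+2 to t+3 |
| each slot t from 78 h to 96 h | t−3 to t+3 | >t−3 to t+3 | none |

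For the 11 slots from 12 h to 72 h the protocol covers 4 h of each 6 h and the SAP covers all 6 h.

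**2. An example.** A subject falls asleep before 16 h and wakes at 20.5 h. The 18 h collection window closed at 20 h and the 24 h window opens at 22 h, so no scheduled score is requested. Table 3 would take a 20.5 h score for the 18 h slot.

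**3. Expected number of missed slots.** The documents give no sleep length, so assume one unbroken sleep of S hours per night, starting at a random point of the 6-hourly grid. Let collection run from 2 h before to u hours after the scheduled time. A slot at t is missed if sleep starts before t−2 and ends after t+u. The values of t for which this happens span S−2−u hours, so

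expected misses per night = max(0, S − 2 − u) / 6.

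| S (h) | Now, u = 2: (S−4)/6 | Up to +3 h, u = 3: (S−5)/6 | Gain |
|---|---|---|---|
| 4 | 0 | 0 | 0 |
| 5 | 0.17 | 0 | 0.17 |
| 6 | 0.33 | 0.17 | 0.17 |
| 7 | 0.50 | 0.33 | 0.17 |
| 8 | 0.67 | 0.50 | 0.17 |
| 9 | 0.83 | 0.67 | 0.17 |

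At 4 h or less there is no gain. Between 4 h and 5 h it is (S−4)/6, and from 5 h upward it is 1/6. A simulation with random phase gave the same gains.

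**4. Total.** 3 nights × 1/6 = 0.5 score per subject, out of 16 scheduled. The primary comparison has 40 + 40 = 80 subjects, so 80 × 0.5 = 40 scores. Half of these subjects are in Cohort 1. If Cohort 1 procedures left nothing to recover there, the total would be 40 × 0.5 = 20.

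**5. Scale against the AUC.** One slot carries about 6 h of the curve. If each imputed value were wrong by a full NRS point in the same direction (an assumption), the mean shift would be 0.5 × 6 × 1 = 3 AUC units. The planned difference is 150 and the SD is 170, so this is 3/150 = 2% of the planned difference. It would largely cancel if it were similar in both arms.

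**The case against.** The strongest reply is that this is a preference, not an error. Analysis windows wider than collection windows are a normal way to keep late scores, and a tighter early collection window is defensible for timing precision. The protocol does not forbid a later score; it only does not ask for one. That stands, and it is why the point is no more than an improvement.

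Several things also make 0.5 per subject an upper figure:

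- Any waking inside the window yields a score.
- In Cohort 1, sensory and motor tests at 8, 12, 24, 30, 48, 60 and 72 h after the block (until recovery is confirmed) need an awake subject, and pain is scored first when assessments coincide (Protocol 12.7, 13.1).
- A subject who wakes and takes breakthrough medication gives an unscheduled score, which can fill the slot.
- Inside an opioid window wWOCF overrides a collected score unless that score is higher.

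Four stronger readings are tempting, and the documents do not support them:

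- **Twice the gain.** Comparing ±2 h with ±3 h on both sides gives (S−4)/6 against (S−6)/6: for S of 6 h or more, 1/3 per night, 1.0 per subject and 80 scores. But scoring on waking extends only the late side, so half of that is available.
- **Imputation from awake subjects only.** The imputation treats all 16 time points jointly, so a missing value is conditioned on the subject's own other scores.
- **The first three nights matter most.** Nothing in the documents says so; the AUC weights all 96 h equally.
- **A biased primary result.** No bias or loss of power has been shown, and step 5 suggests a small effect even under an unfavourable assumption.

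**Conclusion.** The point holds as a cheap improvement. From 12 h to 72 h the plan, followed as written, does not ask for some night scores that its own analysis would accept, and an empty slot is then filled by rule or by model. The size is at most about 0.5 score per subject and about 40 scores in 80 subjects. This rests on three nights before 72 h, one unbroken sleep of 5 h or more in each, and random timing against the schedule. It is zero for sleep of 4 h or less and smaller for the reasons listed above. The effect on the primary AUC is likely to be small. The undefined window in SAP 6.1.1 deserves settling in any case: read with Table 3, a subject waking at +2.5 h is scored; read with Protocol 13.1.1, that subject is not.

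**What to change.** In Protocol 13.1.1, 13.7 and Appendix 1, state that for a subject asleep throughout the window the score is collected on waking, up to 3 h after the scheduled time, with the actual time recorded. In SAP 6.1.1, define the time window as the Table 3 window.

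The cost is a wording change and site instruction. Subjects are in the facility under staff supervision through 96 h (Protocol 13.1, 13.8), so no visit is added, nobody is woken and no analysis method changes. The downside is slightly wider timing of some night scores, which the exact-time AUC already handles.

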13.1.2. Subject Satisfaction with Postsurgical Pain Control

Subject satisfaction with pain management using 1 question from the International Pain Outcome (IPO) questionnaire will be recorded at 96 hours (± 3 h) post-surgery. (see Appendix 2, [Section 18.2](#)).

13.1.3. Pharmacokinetic Assessments (Cohort 1 only)

Blood samples for PK assessment will be obtained from the Cohort 1 subjects. A total of 17 PK samples will be collected for each subject. These samples will be obtained at predose (up to 15 min before block), 30 min (± 5 min), 45 min (± 5 min), and 1 h (± 15 min), 2 h (± 30 min), 8 h (± 30 min), 12 h (± 30 min), 24 h (± 1 h), 30 h (± 1 h), 48 h (± 1 h), 60 h (± 2 h), 72 h (± 2 h), 84 h (± 2 h), 96 h (± 3 h), 120 h (± 3 h), 144 h (± 3 h), and 168 h (± 3 h) from end of block procedure. (See [Table 2](#)).

13.1.4. Pharmacodynamic assessment (Cohort 1 only)

Onset and duration of sensory block will be assessed using the light touch assessment and/or cold sensation to characterize the sensory block (see Appendix 4, [Section 18.4](#)).

Onset and duration of motor block will be assessed using the movement of the foot to characterize the motor block (see Appendix 3, [Section 18.3](#)).

Pharmacodynamic assessments must be performed by trained licensed medical staff (e.g., Physician, Registered Nurse, Physician Assistant) and documented on the investigator’s study delegation log. A limited number of study staff should perform the sensory/motor assessments.

13.2. Study Procedures

13.2.1. Obtaining Informed Consent

Potential subjects undergoing one of the eligible surgeries will be approached by the investigator and/or the study staff for informed consent up to 30 days before the surgery. Subject may be consented on the day of the surgery, if the consent process is started early with ample time for the subject to review the ICF and have all the questions answered by the investigator/study staff prior to providing informed consent.

13.2.2. Screening

Subjects may be screened up to 30 days prior to day of surgery but eligibility should be re-confirmed on day of surgery. Screening procedures that are standard of care at the institution may be completed prior to written informed consent and documented within the 30-day time window. Any screening procedures that are not standard of care must be completed after written informed consent is provided and prior to surgery.

The following screening procedures should be performed after the ICF is signed:

- Explain study purpose and procedures, including responsibilities regarding the e-diary
- Assess eligibility
- Record medical/surgical history
 - As a general guidance, relevant medical/surgical history within the last 5 years (including all ongoing history, regardless of start date) should be recorded in the electronic CRF (eCRF), with the exception of history that is relevant to the lower extremity surgery, in which case all years should be recorded.
 - If a site's standard process includes detailed collection of all history (regardless of relevance/age), only the relevant items should be recorded in the eCRF as outlined above; an asterisk or similar indicator can be used in the source documentation to indicate the relevant items that should be included in the eCRF for source data verification purposes.
- Record prior and concomitant medications
- Record demographics and baseline characteristics including Pain Catastrophizing Scale (PCS) (see Appendix 5, [Section 18.5](#)).
- Record subject height and weight for BMI calculation
- Assess chronic opioid use in the past 30 days
- Conduct urine pregnancy test for women of childbearing potential
- Record AEs/SAEs from the time the ICF is signed
- Record concomitant medications for treatment of AEs

13.2.3. Baseline Procedures (Prior to Study Drug Administration)

- On the day of surgery, before administration of the block, the subject must record responses to the following pain assessments:
 - Pain intensity scores on the NRS as “What was your worst pain in the last 30 days?”
 - Pain intensity scores (using the NRS) “What was your average pain in the last 30 days?”
- Conduct urine pregnancy test for women of childbearing potential
- Record changes to concomitant medications since screening
- Confirm eligibility and randomize subject
- Record AEs/ SAEs and any treatment(s) for the events
- Provide e-diary and instruct the subjects on duties and responsibilities for assessment completion
- For Cohort 1 only:
 - Perform sensory function assessment
 - Perform motor function assessment
 - Obtain blood sample for PK assessment within 15 minutes before block

13.3. Nerve Block Procedure

- Subjects may be lightly sedated with 1 to 2 mg of IV midazolam before the block procedure.
- Administer study drug as combined sciatic (in popliteal fossa) and saphenous (in the adductor canal) nerve blocks using ultrasound 90 min (± 30 min) prior to surgery (unblinded staff only with shielding of the subject’s vision of the study drug syringe)
- Record start and end times of study drug administration
- Record concomitant medications
- Record AEs/ SAEs and any treatment(s) for the events

